6 DOSING DELAYS/DOSE MODIFICATIONS

6.1 Dosing/Delays/Omission/Modification

- The descriptions and grading scales found in the revised NCI Common Terminology Criteria for Adverse Events (CTCAE) version 5.0 will be utilized for dose delays and dose modifications.
- If multiple adverse events are seen, administer dose based on the greatest reduction required for any single adverse event observed. Reductions apply to treatment given in the preceding cycle and are based on adverse events observed since the prior dose.
- If more than one of these apply, use the most stringent (i.e. the greatest dose reduction).
- Dosing interruptions are permitted in the case of medical / surgical events or logistical reasons not related to study therapy (e.g., elective surgery, unrelated medical events, patient vacation, and/or holidays). Participants held for these reasons require prior approval from the PI and should resume therapy within 6 weeks of the scheduled interruption. The reason for interruption should be documented in the participant's study record.

- If treatment is withheld > 8 weeks from the last dose of cabozantinib or nivolumab, the patient should discontinue study therapy.
- For management of AEs which can be clearly attributed to cabozantinib or nivolumab, independent dose modification for either agent is allowed as described. For AEs without clear attribution to either study treatment, management of toxicity should include dose modifications or delay of both agents.
- Participants who require dose delay should be re-evaluated weekly or more frequently if clinically indicated and resume dosing when re-treatment criteria are met.
- Delayed doses of nivolumab and cabozantinib should be administered as soon as the participant meets criteria to resume treatment. If a dose has been delayed, the participant should not wait until the next scheduled dosing date.
- Dosing interruptions will not impact assessments or cycle/day scheduling.
- Restarting of treatment after dose interruption must be discussed with the PI.
- In order to standardize the management of adverse events, treatment management algorithms recommended for utilization in this study are included in Appendix B.

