6.20 Neurologic Events

The principal treatments for neurologic toxicity are dose delay, corticosteroids, and IV immunoglobulin. Patients with any CNS events including aseptic meningitis, encephalitis, symptomatic hypophysitis, myopathy, peripheral demyelinating neuropathy, cranial neuropathy (other than peripheral n. VII), Guillain-Barre syndrome, and myasthenia gravis should discontinue nivolumab. If reversible posterior leukoencephalopathy syndrome (RPLS) is diagnosed then discontinue cabozantinib.

Table: Management of Neurologic Events

Grade	Management
≤ 1	Continue protocol therapy
2	Hold nivolumab. Hold cabozantinib. If treatment with steroids is required, permanently discontinue nivolumab. If no treatment with steroids is required, and it has resolved to \leq Grade 1, resume nivolumab and cabozantinib at same dose. Participants are permitted to resume treatment with nivolumab for peripheral isolated CN VII (Bell's palsy) when stable.
3	Discontinue nivolumab. Hold cabozantinib. If the subject was unequivocally deriving clinical benefit, the subject may be able to resume cabozantinib at a lower dose as determined by the investigator.
4	Discontinue nivolumab. Hold cabozantinib. If the subject was unequivocally deriving clinical benefit, the subject may be able to resume cabozantinib at a lower dose as determined by the investigator.

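### Section 6.20 stops nivolumab for named neurologic syndromes with no grade limit, but its table excludes none of them and continues or resumes nivolumab for milder events

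*Combined protocol and SAP*

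**What the plan says.** Section 6.20 gives its rule twice, in prose and in a table by grade.

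The prose opens its list with "Patients with any CNS events including aseptic meningitis, encephalitis, symptomatic hypophysitis, myopathy, peripheral demyelinating neuropathy" and ends it with "cranial neuropathy (other than peripheral n. VII), Guillain-Barre syndrome, and myasthenia gravis should discontinue nivolumab". No grade is attached. The next sentence concerns the other drug: "If reversible posterior leukoencephalopathy syndrome (RPLS) is diagnosed then discontinue cabozantinib".

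The table is headed for neurologic events as a whole and works by grade:

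- Grade 1 or less: both drugs continue.
- Grade 2: both drugs are held. If steroids are needed, nivolumab stops permanently. The other branch begins "If no treatment with steroids is required, and it has resolved to" grade 1 or less, and its action is to "resume nivolumab and cabozantinib at same dose".
- Grades 3 and 4: nivolumab stops. Cabozantinib is held, and for a patient who is clearly benefiting, "the subject may be able to resume cabozantinib at a lower dose as determined by the investigator".

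The only diagnosis that the table names is Bell's palsy: "Participants are permitted to resume treatment with nivolumab for peripheral isolated CN VII". This matches the exception in the prose.

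**The concern.** For a named syndrome of low grade, one section gives two opposite instructions on the same drug. An investigator who goes straight to the table could keep a patient with mild myasthenia gravis or Guillain-Barre syndrome on nivolumab, although the sentence above the table says to stop. Section 7.1.2 lists myasthenia gravis among the immune-related events already observed. The protocol also provides for external sites (section 4.3 and Appendix D), so different investigators may read the section differently. What is at stake is a patient-safety instruction and how consistently it is applied. The objective response rate (ORR) design is not involved.

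**Working it through.** The plan states no figure here to reproduce, so the check sets the texts side by side.

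**1. Prose against table, nivolumab, for a named syndrome**

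| Situation | 6.20 prose | 6.20 table | Result |
|---|---|---|---|
| Grade 1 or less | stop | continue | conflict |
| Grade 2, no steroids, resolved to grade 1 or less | stop | resume at same dose | conflict |
| Grade 2, steroids required | stop | stop permanently | agree |
| Grade 3 | stop | stop | agree |
| Grade 4 | stop | stop | agree |

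The table has 4 grade rows. Two contain a conflict: the first in full, the second in one of its two branches.

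**2. Which conditions are affected.** The prose names 8: aseptic meningitis, encephalitis, symptomatic hypophysitis, myopathy, peripheral demyelinating neuropathy, cranial neuropathy other than n. VII, Guillain-Barre syndrome and myasthenia gravis. The pituitary note in 6.21 treats symptomatic pituitary enlargement, aseptic meningitis and encephalitis as grade 3. If that note carries over to 6.20, the low-grade rows never apply to the first three. That leaves 8 − 3 = 5 conditions for which the conflict is clearest.

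Hypophysitis has a separate mismatch. The 6.20 prose stops nivolumab when it is symptomatic, whereas the grade 3 row in 6.21 holds nivolumab and resumes it at the same dose.

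**3. Is there a visible precedence rule?**

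- Section 6.1 says "If more than one of these apply, use the most stringent (i.e. the greatest dose reduction". This leans towards stopping, but it is worded for dose reductions and follows a bullet on multiple adverse events. Section 6.2 allows no dose reduction of nivolumab.
- Section 6.1 requires a discussion with the PI before treatment restarts after an interruption. That tempers the grade 2 branch. It does not reach the grade 1 row, where nothing is interrupted.
- Section 6.1 points to the Appendix B algorithms. The neurologic figure is not visible in the text available here, so it can neither settle the point nor count as missing.

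**4. How other diagnosis-based stops are written**

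- 6.5 puts the Hy's law stop inside the grade 2 and grade 3 rows.
- 6.6 limits its continue and resume rows to asymptomatic patients.
- 6.11 has no grade table.
- 6.12 (hypertensive crisis) and 6.15 (nephrotic syndrome) give the stop its own row.
- 6.13 states that arterial thromboembolic events of any grade stop cabozantinib, and it has no grade table.

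None of these six leaves the stop only in prose above unrestricted grade rows, as 6.20 does. Section 6.13 also shows that the plan can name the grade range when it wants to.

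**5. How far the prose reaches.** Its opening words take in CNS events of any kind. Other sections handle some of these differently: 6.13 maintains nivolumab for arterial events, including cerebrovascular ischemia; 6.14 maintains it for CNS hemorrhage; 6.12 only holds it for hypertensive encephalopathy; and the RPLS sentence in 6.20 stops cabozantinib alone. Any repair has to respect these.

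**The case against.** The strongest reply is that an ordinary reading resolves the matter: the prose names diagnoses, and the table is a default by grade. Three features support this.

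- All 4 table rows let cabozantinib continue or resume in some circumstance, so the RPLS sentence would be undercut unless prose prevails.
- The Bell's palsy permission repeats the prose exception, and it makes most sense if other cranial neuropathies may not resume.
- The 6.1 line on stringency points the same way.

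Harm also requires someone to use the row while ignoring the sentence just above it. The grade 2 branch is narrow, because 6.20 counts corticosteroids among the principal treatments and their use already triggers a permanent stop. Section 5.5 lets the treating investigator stop therapy for any relevant change in condition. The Appendix B figure may be explicit.

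Most of this stands, and it lowers the importance of the point. It does not remove the contradiction. The precedence has to be inferred, and because the table names one diagnosis as an exception, a reader could equally infer that the others follow their grade row. Section 6.1 describes the Appendix B algorithms as recommended, and the appendix presents itself as guidance, so even a clear figure would leave two opposite instructions in 6.20.

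**Conclusion.** The inconsistency is real but minor. For nivolumab it is confined to grade 1 or less and to grade 2 events that resolved without steroids, and it is clearest for myopathy, peripheral demyelinating neuropathy, cranial neuropathy other than n. VII, Guillain-Barre syndrome and myasthenia gravis. These counts describe the text, not patient risk. The documents give no frequency for such events, and the trial enrols at most 35 patients.

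Two stronger readings are tempting.

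- A reader might infer that the protocol intends patients with mild named syndromes to stay on nivolumab. The documents do not support that, since the prose and the parallel Bell's palsy exception point the other way.
- A reader might infer that every CNS event should stop nivolumab permanently at any grade. Sections 6.12, 6.13 and 6.14 and the RPLS sentence contradict that.

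The conclusion assumes that the unseen Appendix B figure does not change the wording of 6.20. Sample size, error rates and the primary ORR analysis are unaffected.

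**What to change.** 1. In the 6.20 prose, limit the nivolumab stop to the named immune-mediated syndromes: aseptic meningitis, encephalitis, myopathy, peripheral demyelinating neuropathy, cranial neuropathy other than peripheral n. VII, Guillain-Barre syndrome and myasthenia gravis. Add *permanently, regardless of grade*. Do not attach that phrase to CNS events in general. State that cerebrovascular ischemia follows 6.13, CNS hemorrhage 6.14 and hypertensive encephalopathy 6.12, and that RPLS stops cabozantinib as the prose already says.
2. In the rows for grade 1 or less and grade 2, add *except for the syndromes named above, for which nivolumab is permanently discontinued regardless of grade*. Keep the Bell's palsy allowance.
3. State one rule for symptomatic hypophysitis that serves both 6.20 and 6.21.
4. Check that the Appendix B neurologic algorithm agrees.

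The cost is amendment wording only, with no change to sample size, endpoint or visits. The downside is that a few patients with mild named syndromes would stop nivolumab, which the prose already requires.

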6.21 Endocrinopathy including hypophysitis and adrenal insufficiency

Note all patients with symptomatic pituitary enlargement, exclusive of hormone deficiency, but including severe headache or enlarged pituitary on MRI or aseptic meningitis or encephalitis should be considered grade 3 events. Isolated thyroid or testosterone deficiency may be treated as grade 2 if there are no other associated deficiencies and adrenal function is monitored.

Table: Management of Endocrinopathy including hypophysitis and adrenal insufficiency

Grade	Management
≤ 2	Asymptomatic abnormalities do not require dose delay*. If symptomatic, hold until on a stable replacement hormone regimen. If treated with steroids patients, must be stable off of steroids for two weeks with the exception of adrenal replacement therapy.
3	Hypophysitis: Hold nivolumab and cabozantinib* until \leq Grade 1, then resume at same dose. Other endocrinopathies: Hold nivolumab and cabozantinib* until \leq Grade 1 and stable on replacement hormones, then resume at same dose.

4	
Discontinue nivolumab.
 
Discontinue cabozantinib. If the subject was unequivocally deriving clinical benefit, the subject may be able to resume cabozantinib at a lower dose as determined by the investigator.

---	--

*Patients must be evaluated to rule out pituitary disease prior to initiating thyroid replacement, and steroids including baseline serum: cortisol, ACTH, TSH and free T4

6.22 Thyroid Dysfunction

- Cabozantinib and nivolumab do not need to be held for asymptomatic participants. Management of thyroid dysfunction should follow accepted clinical practice guidelines.
- For **grade 3 hyper- or hypothyroidism**, delay cabozantinib until toxicity improves to grade ≤ 2 , then resume nivolumab and cabozantinib with one dose level reduction.
- For **grade 4 hyper-or hypothyroidism**, discontinue cabozantinib and nivolumab.

6.23 Creatinine Levels/ Renal Insufficiencies

Table: Management of Creatinine Levels/Renal Insufficiencies

Grade	Management
≤ 1	Continue protocol therapy. Monitor weekly until return to baseline.
2-3 (>1.5 baseline to $\leq 6.3.0 \times$ ULN)	Hold nivolumab and cabozantinib until \leq Grade 1. Monitor creatinine every 2-3 days. Start 0.5 to 1.0 mg/Kg/day methylprednisolone IV or oral equivalent. Consider consulting nephrology and obtaining a renal biopsy.
4 ($>6.0 \times$ ULN)	Discontinue nivolumab and hold cabozantinib. Monitor creatinine daily. Start 1.0 – 2.0 mg/Kg/day methylprednisolone IV or oral equivalent. Consult nephrologist and consider obtaining a renal biopsy.

6.24 Infusion Reactions

All Grade 3 or 4 infusion reactions should be reported within 24 hours to the study PI and reported as an SAE if criteria are met. Infusion reactions should be graded according to National Cancer Institute Common Terminology Criteria for Adverse Events (NCI CTCAE (version 5.0)) guidelines. Treatment recommendations are provided below and may be modified based on local treatment standards and guidelines as appropriate:

Table: Management of Infusion Reaction

Grade	Management
≤ 1	Continue nivolumab infusion, remain at bedside. Continue cabozantinib.

	Institute prophylactic medications with subsequent infusions.
2	Hold nivolumab until resolution to \leq Grade 1. Refer to management and rechallenging instructions below. Continue cabozantinib.
3	Discontinue nivolumab. Continue cabozantinib.
4	Discontinue nivolumab. Continue cabozantinib.

For Grade 1 symptoms:

Mild reaction; infusion interruption not indicated; intervention not indicated

Remain at bedside and monitor subject until recovery from symptoms. The following prophylactic premedications are recommended for future infusions: diphenhydramine 50 mg (or equivalent) and/or paracetamol 325 to 1000 mg (acetaminophen) at least 30 minutes before additional nivolumab administrations.

For Grade 2 symptoms: Moderate reaction requires therapy or infusion interruption but responds promptly to symptomatic treatment [eg, antihistamines, non-steroidal anti-inflammatory drugs, narcotics, corticosteroids, bronchodilators, IV fluids]; prophylactic medications indicated for \leq 24 hours).

Stop the nivolumab infusion, begin an IV infusion of normal saline, and treat the subject with diphenhydramine 50 mg IV (or equivalent) and/or paracetamol 325 to 1000 mg (acetaminophen); remain at bedside and monitor subject until resolution of symptoms. Corticosteroid or bronchodilator therapy may also be administered as appropriate. Restart the infusion at 50% of the original infusion rate when symptoms resolve to Grade \leq 1; if no further complications ensue after 30 minutes, the rate may be increased to 100% of the original infusion rate. Monitor participant closely. If symptoms recur then no further nivolumab will be administered at that visit. Administer diphenhydramine 50 mg IV, and remain at bedside and monitor the participant until resolution of symptoms. The amount of study drug infused must be recorded on the electronic case report form (eCRF). The following prophylactic premedications are recommended for future infusions: diphenhydramine 50 mg (or equivalent) and/or paracetamol 325 to 1000 mg (acetaminophen) should be administered at least 30 minutes before additional nivolumab administration. If necessary, corticosteroids (recommended dose: up to 25 mg of IV hydrocortisone or equivalent) may be used.

For Grade 3 or Grade 4 symptoms:

Grade 3: prolonged [ie, not rapidly responsive to symptomatic medication and/or brief interruption of infusion]; recurrence of symptoms following initial improvement; hospitalization indicated for other clinical sequelae [eg, renal impairment, pulmonary infiltrates].

Grade 4: life-threatening; pressor or ventilatory support indicated.

Immediately discontinue infusion of nivolumab. Begin an IV infusion of normal saline, treat with bronchodilators, epinephrine 0.2 to 1 mg of a 1:1,000 solution for subcutaneous administration or 0.1 to 0.25 mg of a 1:10,000 solution injected slowly for IV administration, and/or diphenhydramine 50 mg IV with methylprednisolone 100 mg IV (or equivalent), as needed. Participant should be monitored until the investigator is comfortable that the symptoms will not recur.

Investigators should follow their institutional guidelines for the treatment of anaphylaxis. Remain at bedside and monitor subject until recovery from symptoms. In the case of late-occurring hypersensitivity symptoms (e.g., appearance of a localized or generalized pruritis within 1 week after treatment), symptomatic treatment may be given (e.g., oral antihistamine, or corticosteroids)

6.25 Fever

Patients with fever should be evaluated as clinically appropriate. Patients may experience isolated fever during infusion reactions or up to several days after infusion. Evaluation over the course of 1-2 weeks should be done for other autoimmune events that may present as fever.

Table 16: Management of Fever

Grade	Management
≤1	Continue nivolumab and cabozantinib and monitor.
2	Hold nivolumab and cabozantinib until ≤ Grade 1
3	Hold nivolumab and cabozantinib until ≤ Grade 1
4	Hold nivolumab and cabozantinib until ≤ Grade 1

6.26 Management of other toxicities attributable to cabozantinib

General guidance for management of non-hematologic toxicity not described above and considered at least possibly related to cabozantinib only:

CTCAE v.5.0 Grade	Recommended Guidelines for Management ^a
Grade 1 AEs	Add supportive care as indicated. Continue cabozantinib treatment at the current dose level if AE is manageable and tolerable. Continue nivolumab
Grade 2 AEs which are tolerable and are easily managed	Continue cabozantinib treatment at the current dose level with supportive care. Continue nivolumab.
Grade 2 AEs which are intolerable and cannot be adequately managed	At the discretion of the investigator, cabozantinib should be dose reduced or interrupted. Note: It is recommended that dose holds be as brief as possible.
Grade 3 AEs (except clinically non-relevant laboratory abnormalities)	Cabozantinib should be interrupted unless the toxicity can be easily managed with a dose reduction and optimal medical care. Continue nivolumab. Note: It is recommended that dose holds be as brief as possible.
Grade 4 AEs (except clinically non-relevant laboratory abnormalities)	Subjects should have cabozantinib interrupted immediately. Discontinue cabozantinib unless the following criteria are met: 
 • Subject is deriving clear clinical benefit as determined by the investigator • Toxicity can be managed with a dose reduction following recovery to Grade 1 (or baseline) and optimal medical care Continue nivolumab.

AE, adverse event.

^a Study treatment dose adjustment is only needed if the toxicity was deemed related to cabozantinib treatment or had an unclear relationship to cabozantinib treatment.

6.27 Management of other toxicities attributable to nivolumab

General guidance for management of other non-laboratory adverse events not described above attributed to nivolumab only:

Grade	Management/Next Dose for Nivolumab
≤ 1	Continue protocol therapy.
2	Hold nivolumab until ≤ Grade 1 OR baseline (exceptions as noted below). Continue cabozantinib.
3	Omit dose of nivolumab if not recurrent (exceptions as noted below). Continue

Grade	Management/Next Dose for Nivolumab
	cabozantinib.
4	Discontinue nivolumab therapy. Continue cabozantinib.
Recommended management: Low-grade events that are considered drug related and any high-grade events of unclear etiology should be fully evaluated and treated with systemic corticosteroids if an alternative etiology is not identified.	

7 ADVERSE EVENTS: LIST AND REPORTING REQUIREMENTS

Adverse event (AE) monitoring and reporting is a routine part of every clinical trial. The following list of reported and/or potential AEs (Section 7.1) and the characteristics of an observed AE (Section 7.2) will determine whether the event requires expedited reporting **in addition** to routine reporting.

7.1 Adverse Events Lists

7.1.1 Expected adverse events for cabozantinib

The general adverse event profile of cabozantinib includes GI symptoms (such as nausea, vomiting, and diarrhea), fatigue, anorexia, palmar-plantar erythrodysesthesia (PPE) syndrome, skin rash, elevated ALT and AST, increased pancreatic enzymes with rare cases of pancreatitis, as well as side effects associated with inhibition of VEGF signaling such as thrombotic events (eg, pulmonary embolism [PE] and deep vein thrombosis [DVT]), hypertension, proteinuria, hemorrhagic events, and rare cases of gastrointestinal [GI] perforation and rectal/perirectal abscess. Additionally, events of arterial thromboembolism (transient ischemic attack [TIA], myocardial infarction [MI]) have been reported. For a full listing of safety events please refer to the Cabozantinib Investigational Brochure.

7.1.2 Expected adverse event for nivolumab

The PD-L1/PD-1 pathway is involved in peripheral tolerance; therefore, such therapy may increase the risk of immune-related AEs, specifically the induction or enhancement of autoimmune conditions. AEs with potentially immune-related causes, including rash, hypothyroidism, hepatitis/transaminitis, colitis, myositis, and myasthenia gravis, have been observed.

7.2 Adverse Event Characteristics

- **CTCAE term (AE description) and grade:** The descriptions and grading scales found in the revised NCI Common Terminology Criteria for Adverse Events (CTCAE) version 5.0 will be utilized for AE reporting. All appropriate treatment areas should have access to a copy of the CTCAE version 5.0. A copy of the CTCAE version 5.0 can be downloaded from the CTEP web site http://ctep.cancer.gov/protocolDevelopment/electronic_applications/ctc.htm.

- **For expedited reporting purposes only:**
 - AEs for the agent(s) that are listed above should be reported only if the adverse event varies in nature, intensity or frequency from the expected toxicity information which is provided.
 - Other AEs for the protocol that do not require expedited reporting are outlined in the next section (Expedited Adverse Event Reporting) under the sub-heading of Protocol-Specific Expedited Adverse Event Reporting Exclusions.
- **Attribution of the AE:**
 - Definite – The AE is *clearly related* to the study treatment.
 - Probable – The AE is *likely related* to the study treatment.
 - Possible – The AE *may be related* to the study treatment.
 - Unlikely – The AE is *doubtfully related* to the study treatment.
 - Unrelated – The AE is *clearly NOT related* to the study treatment.

